## **2 OBJECTIVES**

### **2.1 Primary Objective:**

- 2.1.1 To estimate the efficacy of sEphB4-HSA in patients with mCRPC as measured by confirmed PSA response rate.

### **2.2 Secondary Objectives:**

- 2.2.1 The safety and tolerability of sEphB4-HSA in patients with mCRPC according to NCI CTCAE v 5.0 (See Appendix II).
- 2.2.2 To assess the time to PSA progression.
- 2.2.3 To assess overall response rate in patients with measurable disease using RECIST 1.1 (soft tissue) and PCWG3 (bone) criteria.
- 2.2.4 To assess radiological progression free survival (rPFS) using RECIST 1.1 (soft tissue) and PCWG3 (bone) criteria.

### **2.3 Exploratory Objectives:**

- 2.3.1 To explore molecular changes associated with EphB4 and ephrinB2 expression in tumor specimens (primary and/or metastatic tissue).
- 2.3.2 To explore association of response with molecular biomarkers including aberrations in the PI3K pathway, MYC and TP53.
- 2.3.3 To assess immune cell infiltration of tumors in archival tissue, if tissue is available.
- 2.3.4 To assess circulating immune changes associated with treatment.

## **3 PATIENT ELIGIBILITY**

The target population for this study are patients with mCRPC who have progressive disease despite castrate levels of testosterone (<50 ng/dL) and have received at least one standard first-line therapy for metastatic castrate resistant prostate cancer, which can include therapy with a 2nd generation AR targeted therapy (abiraterone or enzalutamide) or chemotherapy (docetaxel or cabazitaxel). This study will be a multicenter trial conducted at Northwestern University and will serve as the lead site and coordinating center for the study. Participating sites include University of Chicago and University of Southern California.

A total of 25 evaluable subjects will be needed for this trial. Approximately 4-8 potentially eligible patients are seen per month, and it is anticipated that at least 1-2 per month will be accrued (once all sites are up and running).

Eligibility will be evaluated by the study team according to the following criteria. Eligibility waivers are not permitted. Subjects must meet all of the inclusion and none of the exclusion criteria to be registered to the study. Study treatment may not begin until a subject is registered. Please refer to Section 11 for complete instructions regarding registration procedures.

### **3.1 Inclusion Criteria**

- 3.1.1 Patients must have a pathologically confirmed diagnosis of prostate adenocarcinoma
- 3.1.2 Patients must have metastatic (M1) disease as evidenced by soft tissue and/or bony metastases on CT or MRI scan or technetium bone scan.

**NU Study Number:** NU 18U10

3.1.3 Patients must have castration resistant disease with disease progression despite castrate levels of testosterone (testosterone  $\leq$  50 ng/dL)

3.1.4 Patients must have received and progressed on at least one second generation AR targeted therapy for castration resistant disease irrespective of prior chemotherapy. No more than 3 prior treatment therapies for castration resistant disease (life prolonging) are permitted. Prior therapy can include:

- Second generation AR targeted therapy [i.e. abiraterone, enzalutamide, or other new antiandrogen (ODM-201, apalutamide)]
- Chemotherapy (docetaxel and/or cabazitaxel).

3.1.5 Documented progressive mCRPC based on at least one of the following criteria:

- PSA progression defined as 25% increase over baseline value with an increase in the absolute value of at least 2.0 ng/mL that is confirmed by another PSA level with a minimum of a 1 week interval and a minimum PSA of 2.0 ng/mL.
- Progression of bidimensionally measurable soft tissue or nodal metastasis assessed within one month prior to registration by a CT scan or MRI. (Please refer to Section 6.1.2 for definition of measurable disease.)
- Progression of bone disease (evaluable disease) (new bone lesion(s)) by bone scan.

3.1.6 Serum testosterone  $<$  50 ng/dL. Patients must continue primary ADT with an LHRH analogue (agonist or antagonist) if they have not undergone orchiectomy.

3.1.7 Patients must be age  $\geq$  18 years.

3.1.8 Patients must have an ECOG performance status of 0-2 (See Appendix I Section 12.1)

3.1.9 Patients must have adequate organ and bone marrow function as defined below within 2 weeks prior to registration:

Absolute Neutrophil Count	$\geq$ 1,000/mcL
Hemoglobin	$\geq$ 9 g/dL*
Bilirubin	$\leq$ 1.5 x institutional upper limit of normal (ULN) except for unconjugated hyperbilirubinemia or Gilbert's Syndrome, who can have total bilirubin $<$ 3.0 mg/dL.
AST/ALT	$\leq$ 3 x ULN ( $\leq$ 5 x ULN if liver metastases present)
Serum Creatinine	$\leq$ 2.0 X ULN (upper limit of normal) or creatinine clearance $\geq$ 30 mL/minute (using Cockcroft/Gault formula)
Platelet	$>$ 100,000

\* Transfusion is allowed as long as patients have not received prior transfusion  $\leq$  28 days from registration.

3.1.10 Patients must use a condom during treatment and for 3 months after the last dose of study treatment when having sexual intercourse. Female partners of male subjects should also use a highly effective form of contraception if they are of

**NU Study Number:** NU 18U10

childbearing potential (See Appendix III Section 12.3). Subjects should not donate sperm throughout the study and for 3 months following the last dose of treatment.

3.1.11 Patients must have the ability to understand and the willingness to sign a written informed consent prior to registration on study.

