**3.2 Exclusion Criteria**

3.2.1 Patients who have received more than 3 prior treatment therapies (life prolonging) for mCRPC are not eligible.

3.2.2 Patients who have had radiotherapy  $\leq 14$  days prior to entering the study are not eligible.

*Note: Palliative radiation therapy is allowed.*

3.2.3 Patients who have had systemic therapy for prostate cancer  $\leq 21$  days or 5-half lives (whichever is shorter) are not eligible.

*Note: Patients can receive a stable dose of bisphosphonates for bone metastases, including zoledronic acid, or denosumab before and during the study as deemed appropriate by the treating physician. Patients must continue Androgen Deprivation Therapy.*

3.2.4 Patients receiving any other investigational agents are not eligible.

3.2.5 Patients with Small cell carcinoma of the prostate are not eligible.

*Note: Neuroendocrine differentiation is permitted. If there is doubt about this and it is clinically indicated then a biopsy should be obtained to document histological differentiation.*

3.2.6 Patients who have a history of allergic reactions attributed to compounds of similar chemical or biologic composition to sEphB4-HSA are not eligible.

AND

Patients who have had prior exposure to compounds of similar chemical or biologic composition to sEphB4-HSA are not eligible.

3.2.7 Patients who have an uncontrolled intercurrent illness including, but not limited to any of the following, are not eligible:

- Ongoing or active infection requiring systemic treatment
- Symptomatic congestive heart failure (New York Heart Association Class III or IV congestive heart failure)
- Unstable angina pectoris
- Serious cardiac arrhythmia

3.2.8 Patients with uncontrolled hypertension (defined as systolic BP  $\geq 160$  mmHg or diastolic BP  $\geq 95$  mmHg) are not eligible.

*Note: Patients with a history of hypertension are allowed provided blood pressure is controlled by anti-hypertensive treatment*

3.2.9 Patients with Electrocardiogram (ECG) with QT interval (QTc)  $> 480$  msec are not eligible.

3.2.10 Patients with other malignancy that has progressed or has required active systemic treatment in the last 3 years.

**NU Study Number:** NU 18U10

*Note: Patients with basal cell carcinoma of the skin, squamous cell carcinoma of the skin that has undergone potentially curative therapy or carcinoma in situ or non-muscle invasive bladder cancer are not excluded.*

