## **6 ENDPOINT ASSESSMENT**

### **6.1 Definitions**

#### **6.1.1 Evaluable patients**

Evaluable for primary endpoint of PSA response. All patients who received at least 1 dose of the study drug and who also had a followup PSA test conducted prior to initiating subsequent therapy will be evaluable for PSA response.

Evaluable for toxicity. All patients who received at least 1 dose of the study drug will be evaluable for toxicity.

Evaluable for objective response. Only those patients who have measurable disease present at baseline will be considered evaluable for objective response. These patients will have their response classified according to the definitions stated below.

Evaluable Non-Target Disease Response. Patients who have lesions present at baseline that are evaluable but do not meet the definitions of measurable disease will be considered evaluable for non-target disease. The response assessment is based on the presence, absence, or unequivocal progression of the lesions.

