## 6.2 Assessment of primary endpoint

The assessment of the primary endpoint of confirmed PSA response rate is defined as the proportion of subjects who received at least 1 dose of the study drug achieving a post-treatment PSA partial response or complete response as defined by PSA response criteria in section 6.1.5

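### Patients who enter on soft-tissue or bone progression need no minimum PSA, although PSA response is the sole primary endpoint

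*Combined protocol and SAP*

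**What the plan says.** Section 3.1.5 admits a patient with "Documented progressive mCRPC based on at least one of the following criteria", and lists three routes.

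- **PSA route:** a 25% rise and an absolute rise of at least 2.0 ng/mL, "confirmed by another PSA level with a minimum of a 1 week interval and a minimum PSA of 2.0 ng/mL".
- **Soft-tissue route:** "Progression of bidimensionally measurable soft tissue or nodal metastasis assessed within one month prior to registration by a CT scan or MRI". No PSA condition.
- **Bone route:** "Progression of bone disease (evaluable disease) (new bone lesion(s)) by bone scan". No PSA condition.

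No other criterion in 3.1 or 3.2 sets a PSA level. The calendar in Section 5 has PSA drawn at screening, without a threshold.

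For the primary endpoint, 6.1.1 requires one dose and says that patients "who also had a followup PSA test conducted prior to initiating subsequent therapy will be evaluable for PSA response". Section 6.2 defines the rate as "the proportion of subjects who received at least 1 dose of the study drug achieving a post-treatment PSA partial response or complete response". Neither sets a baseline PSA. By contrast, 6.1.1 restricts objective response to patients with measurable disease at baseline.

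Section 6.1.5 defines PSA partial response as a confirmed fall of at least 50%, with no minimum starting value. PSA complete response is a confirmed value of 0.2 ng/mL or less, with no fall from baseline required. PSA progression needs a 25% rise over baseline or nadir, whichever is lower, and an absolute rise of 2 ng/mL.

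Section 10.1 bases both decisions on PSA response: continue with 2 or more responders in 15, and declare success with 6 or more in 25.

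**The concern.** The plan has a PSA minimum, but only on the route where it adds nothing: a rise of at least 2.0 ng/mL cannot end below 2.0 ng/mL. On the two imaging routes, where it could exclude someone, it is absent. A patient whose PSA is very low at the start can therefore take one of the 15 or 25 places on which the whole decision rests.

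The error can go either way. If such patients are less able to show a PSA fall, a useful drug is more likely to be missed. If they qualify as responders on a tiny change, or on no change, an inactive drug is more likely to pass. The plan guards against the parallel problem for objective response by requiring measurable disease, but has no counterpart for the endpoint that decides the trial.

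**Working it through.** **Inputs.** From 10.1: p0 = 0.10, p1 = 0.30, 15 patients in stage 1 with 2 or more responses to continue, 25 in total with 6 or more for success. From 6.1.5: the PSA response and progression definitions. Assumed: k, the share of low-PSA patients, and q, their response rate. The documents give neither.

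**1. The plan's own figures.** For a response rate p,

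P(success) = Σ over x = 2 to 15 of Bin(15, x, p) × P(Bin(10, p) ≥ 6 − x).

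- p = 0.10: 0.0328 (plan: alpha 0.033).
- p = 0.30: 0.8017 (plan: beta 0.198, so power 0.802).
- Stopping after stage 1 at p = 0.10: 0.9^15 + 15 × 0.1 × 0.9^14 = 0.2059 + 0.3432 = 0.549 (plan: 0.549).

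All reproduce. Power exceeds 80% by only 0.2 points.

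**2. Effect on power.** With a 30% rate in the other patients, the average rate is p = 0.30(1 − k) + qk.

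| k | q | p | Power |
|---|---|---|---|
| 0 | any | 0.300 | 80.2% |
| 4% (on average 1 of 25) | 0 | 0.288 | 76.4% |
| 4% | 20% | 0.296 | 79.0% |
| 4% | 30% | 0.300 | 80.2% |
| 12% (on average 3 of 25) | 0 | 0.264 | 67.5% |
| 12% | 20% | 0.288 | 76.4% |
| 12% | 30% | 0.300 | 80.2% |

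The rows with q = 0 are the extreme case. Under 6.1.5 a fall from 0.8 to 0.4 ng/mL, if confirmed, is a partial response, so a low PSA does not itself rule out a response.

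**3. Effect on type I error.** Take exactly one stage 1 patient who enters on imaging with PSA at or below 0.2 ng/mL and stays there. Read literally, 6.1.5 makes this a complete response. The other 14 stage 1 patients then need 1 response to continue, and all 24 others need 5 for success. At a true 10% rate in those 24:

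P(success) = Σ over x = 1 to 14 of Bin(14, x, 0.1) × P(Bin(10, 0.1) ≥ 5 − x).

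- x = 1: 0.3559 × 0.0128 = 0.0046
- x = 2: 0.2570 × 0.0702 = 0.0180
- x = 3: 0.1142 × 0.2639 = 0.0301
- x = 4: 0.0349 × 0.6513 = 0.0227
- x ≥ 5: 0.0092

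The unrounded sum is 0.0847, or 8.5%, against 3.3% with no such patient and a stated limit of 5%. The chance of passing stage 1 rises from 1 − 0.549 = 45.1% to 1 − 0.9^14 = 77.1%.

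**4. Time to PSA progression.** From a baseline of 0.8 ng/mL with no lower nadir, PSA must reach 0.8 + 2 = 2.8 ng/mL, a rise of 2.8/0.8 = 3.5-fold. From 2.0 ng/mL it must reach 4.0, a 2-fold rise. From 8 ng/mL upward the 25% rule governs, since 2/0.25 = 8. The time is therefore biased long at low baselines.

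**The case against.** The strongest reply is that nothing in the statistical section is wrong. Section 10.1 sets 30% as the response rate of the trial population, not of patients with informative PSA, and for that input 80.2% is correct. Power falls only if 30% is read as the rate in a subgroup that the plan never defines. This stands: step 2 shows sensitivity to an assumption and is not a correction of the sample size.

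A reader might infer that the trial is underpowered, at 67.5% or less. The documents do not support that. It needs both a sizeable k and no chance of response in low-PSA patients; k is undocumented, may be zero, and 6.1.5 lets such patients respond.

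A reader might also point to the note in 3.2.5, "Neuroendocrine differentiation is permitted", as evidence that low-PSA patients are expected. The documents nowhere link that feature to low PSA, so the point does not rely on it.

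It can also be said that an assessor would hardly call an unchanged PSA of 0.2 ng/mL a response. Perhaps so, but the definition as written counts it, and the decision should not depend on someone departing from the text.

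Further, 2.0 ng/mL belongs to a definition of progression and is not put forward as a threshold for a measurable PSA, and a floor will not catch every patient whose PSA fails to follow the tumour. Both are true. The floor does prevent unchanged or trivial values from counting as responses. Finally, growth without a PSA rise is picked up by rPFS (6.3.4), and time to PSA progression is secondary, with no decision rule, so that part is minor.

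**Conclusion.** The gap is real: no baseline PSA is required of imaging-route patients in eligibility, evaluability or the response definition, while PSA response alone drives both Simon decisions. The design figures themselves are correct.

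The size and net direction cannot be determined from the documents. If k is zero there is no effect. At k = 4% power lies between 76.4% and 80.2% as the response rate in low-PSA patients runs from 0 to 30%. In the other direction, a single stage 1 patient who starts and remains at or below 0.2 ng/mL takes type I error from 3.3% to 8.5%, above the stated limit. That figure assumes the complete-response definition is applied literally and a 10% rate in the other 24 patients. It shows what the wording allows; it does not predict that such a patient will enrol. Because the prevention is cheap, the change is worth making.

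**What to change.** - **Patients not yet enrolled:** make a screening PSA of at least 2.0 ng/mL, the figure already in 3.1.5, a separate inclusion criterion for all three routes.
- **Patients already enrolled** (the Amendment 5 entry in Appendix V shows there are some): keep them in the primary analysis, report baseline PSA, and add a sensitivity analysis restricted to baseline PSA of at least 2.0 ng/mL.
- **Section 6.1.5:** state that PSA complete response also requires a fall of at least 50% from baseline. At or above the floor this changes nothing, since going from 2.0 to 0.2 ng/mL is already a 90% fall. It matters for enrolled patients below the floor.

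The cost is a short amendment; PSA is already drawn at screening. The few imaging-only progressors with PSA below 2.0 ng/mL are lost, and eligibility will differ before and after the amendment, which the report should state. The floor reduces the bias in time to PSA progression but does not remove it.

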**3.2 Exclusion Criteria**

3.2.1 Patients who have received more than 3 prior treatment therapies (life prolonging) for mCRPC are not eligible.

3.2.2 Patients who have had radiotherapy  $\leq 14$  days prior to entering the study are not eligible.

*Note: Palliative radiation therapy is allowed.*

3.2.3 Patients who have had systemic therapy for prostate cancer  $\leq 21$  days or 5-half lives (whichever is shorter) are not eligible.

*Note: Patients can receive a stable dose of bisphosphonates for bone metastases, including zoledronic acid, or denosumab before and during the study as deemed appropriate by the treating physician. Patients must continue Androgen Deprivation Therapy.*

3.2.4 Patients receiving any other investigational agents are not eligible.

3.2.5 Patients with Small cell carcinoma of the prostate are not eligible.

*Note: Neuroendocrine differentiation is permitted. If there is doubt about this and it is clinically indicated then a biopsy should be obtained to document histological differentiation.*

3.2.6 Patients who have a history of allergic reactions attributed to compounds of similar chemical or biologic composition to sEphB4-HSA are not eligible.

AND

Patients who have had prior exposure to compounds of similar chemical or biologic composition to sEphB4-HSA are not eligible.

3.2.7 Patients who have an uncontrolled intercurrent illness including, but not limited to any of the following, are not eligible:

- Ongoing or active infection requiring systemic treatment
- Symptomatic congestive heart failure (New York Heart Association Class III or IV congestive heart failure)
- Unstable angina pectoris
- Serious cardiac arrhythmia

3.2.8 Patients with uncontrolled hypertension (defined as systolic BP  $\geq 160$  mmHg or diastolic BP  $\geq 95$  mmHg) are not eligible.

*Note: Patients with a history of hypertension are allowed provided blood pressure is controlled by anti-hypertensive treatment*

3.2.9 Patients with Electrocardiogram (ECG) with QT interval (QTc)  $> 480$  msec are not eligible.

3.2.10 Patients with other malignancy that has progressed or has required active systemic treatment in the last 3 years.

**NU Study Number:** NU 18U10

*Note: Patients with basal cell carcinoma of the skin, squamous cell carcinoma of the skin that has undergone potentially curative therapy or carcinoma in situ or non-muscle invasive bladder cancer are not excluded.*

3.2.11 Patients with known active CNS metastases and/or carcinomatous meningitis are not eligible.

*Note: A scan to confirm the absence of brain metastases is not required. Subjects with previously treated brain metastases may participate provided they are stable, i.e. without evidence of progression for at least 4 weeks by repeat imaging (note that the repeat imaging should be performed during study screening), without requirement of steroid treatment for at least 4 weeks prior to randomization and with any neurologic symptoms resolved or have returned to baseline of prior treatment for brain metastasis*

3.2.12 Patients with spinal cord compression are not eligible unless considered to have received definitive treatment for this and evidence of stable disease for 28 days.

3.2.13 Patients who underwent major surgery  $\leq$ 14 days of starting study treatment or have not recovered from effects of surgery are not eligible.

3.2.14 Patients with a history of significant thromboembolic events, (including recurrent DVT, CVAs, or recurrent pulmonary embolism) are not eligible.

3.2.15 Patients with a history of any of the following are not eligible:

- History of noncompliance with other medical therapy for medical conditions that could be impacted by study drug-related adverse events.
- An illness, condition, or other situation that the treating investigator feels would limit compliance with study requirements or would comprise the subject's safety or study endpoints.

## 4 TREATMENT PLAN

### 4.1 Overview

This study plans to enroll two successive cohorts by a Simon two-stage design of 15 and 10 evaluable patients, for possible total of 25 evaluable patients with progressive mCRPC after treatment with at least one first-line therapy for metastatic castration-resistant prostate cancer including new AR targeted therapy (i.e. abiraterone, enzalutamide or similar agents) or chemotherapy (docetaxel or cabazitaxel or noavel taxane). The second cohort will be recruited if the first cohort shows a signal of activity and no signs of unexpected toxicity; see section 6.1 for definitions.

- Patients will receive sEphB4-HSA 1000mg IV ( $60 \pm 15$  min infusion) on day 1 in a 14-day cycle along with continuation of androgen deprivation therapy. Assessment of response to therapy with PSA will be every odd cycle (every 28 days). Imaging will occur at baseline and 2 months after starting therapy; thereafter, imaging will be conducted every 3 months. After 1 year, imaging can be done every 4 months for patients with stable disease or better. Scans may also be conducted at any time, if clinically indicated. Beginning at Cycle 7, cycle length will be 21 days and patients will return for treatment on Day 1 of each cycle.

*Note: patients will receive ADT per treating physician's choice (LHRH agonist/antagonist or orchiectomy) as standard therapy.*

NU Study Number: NU 18U10

- Cell Free DNA (cfDNA) will be collected at baseline and on Day 1 of cycle 5, and at disease progression or end of treatment for molecular analysis. We will collect serum for cytokine panel analysis (TNFa, IL1beta, IL2, 4, 5, 6, 8, 10, 12, 13) at baseline Day 1 of cycle 5 prior to drug infusion and at disease progression or end of treatment.

Patients may continue to receive sEphB4-HSA treatment until no longer clinically benefiting (PCWG3), unacceptable toxicity, treatment delay  $\geq 4$  weeks, or prohibitive illness/change in patient's condition, or patient decides to withdraw from study. Response assessment with PSA will occur every odd cycle (28 days). Imaging will occur at baseline and 2 months after starting therapy; thereafter, imaging will be conducted every 3 months. After 1 year, imaging can be done every 4 months for patients with stable disease or better. Scans may also be conducted at any time, if clinically indicated. Once off treatment continue follow-up for 4 weeks or resolution/stabilization of AE. Patients will be followed every 6 months, until objective progression, or 1 year.

